### **6.2.2 Statistical Plan for Preliminary Analyses**

The study team, led by our statisticians, will compute descriptive statistics (mean, standard deviation, and 95% confidence interval) for change scores from baseline to post-treatment on the COSS-P and COSS-T in raw score format (mean item score). Descriptive statistics will be computed for each of the two arms of the study (OST-S, TAU-WL), as well as each grade-level subgroup (Grade 3, 4, 5) and school resource-level subgroup (low, middle, high subsidized lunch rate) within each arm. These descriptive statistics will be highly valuable in determining whether there is a signal of overall OST-S effectiveness, differential effects for grade-level subgroups, and differential effects for schools with low, middle, and high subsidized lunch rates. The study team will evaluate whether the lower limit of 95% confidence intervals is above 0, which would be suggestive of a significant difference. In addition, the difference in mean change scores between study conditions will be divided by the standard deviation of the control group (TAU-WL) standard deviation of change scores to provide a rough estimate of effect size for the entire sample, each grade-level subgroup, and each school subsidized lunch rate subgroup. Further, descriptive statistics will be computed to characterize the OST-S and TAU-WL conditions with regard to child sex, grade level, and school subsidized lunch rate subgroup.

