In addition, we will determine whether there is a difference between intervention conditions with regard to the proportion of students who demonstrate a small, medium, and large degree of change in the expected direction from baseline to post-treat, as well as the proportion of students who demonstrate no change and change in the opposite direction. Degree of change on each measure (COSS-P and COSS-T) will be computed for each participant by subtracting baseline score from post-treatment score and dividing by the standard deviation of change scores for the condition to which the participant was assigned (OST-S vs. TAU-WL). Similar to guidelines established by Cohen (1988), effect sizes (ES) approximating .20 will be considered small; ES approximating .50 will be medium; and ES approximating .80 or higher will be large. We will conduct these analyses with all students in OST-S and TAU-WL as well as with subgroups based on grade level and subsidized lunch rate. **Because we did not include a plan to examine the proportion of students**

**responding to each condition in the original analytic plan, we are including a request for these analyses in this amendment.**

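### Degree-of-change categories are scaled by each arm's own SD, so when the arm SDs differ the compared proportions do not show whether more students improved by a given amount

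*Protocol*

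**What the plan says.** Protocol section 6.2.2 sets out two standardised summaries of change from baseline to post-treatment on the COSS-P and COSS-T.

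- **Group effect size.** The difference between arms in mean change "divided by the standard deviation of the control group (TAU-WL) standard deviation of change scores". The scale is the control arm's SD of change.
- **Degree of change for each student.** The stated aim is a comparison of arms: "we will determine whether there is a difference between intervention conditions with regard to the proportion of students who demonstrate a small, medium, and large" change, as well as no change or change in the opposite direction. Each student's change is graded after "dividing by the standard deviation of change scores for the condition to which the participant was assigned". The cut-offs are the same numbers in both arms: "effect sizes (ES) approximating .20 will be considered small; ES approximating .50 will be medium", and "ES approximating .80 or higher will be large". The tabulation is repeated by grade and by subsidized-lunch subgroup.

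The underlying scores are on a raw scale shared by both arms ("change scores from baseline to post-treatment on the COSS-P and COSS-T in raw score format (mean item score")). The section does not say that the arm SDs are assumed equal, and it gives no common denominator for the categories. It also does not say whether the SDs are recomputed within subgroups.

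The SAP does not use this rule. It classifies students by normative or scale thresholds that are the same in both arms, and it divides by the combined baseline SD for Cohen's d.

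**The concern.** A comparison of responder proportions is useful only if a responder means the same thing in both arms. Here the standardised cut-off is fixed but the unit is not: a cut-off of 0.80 means 0.80 OST-S SDs for one student and 0.80 TAU-WL SDs for another. Two students with identical raw change can be graded differently solely because of assignment.

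Unequal SDs are quite possible. If students respond unevenly to OST-S, its change scores will spread more widely than those of TAU-WL, and its students will need a larger raw gain to reach each category. If the OST-S SD is the smaller one, the rule works in favour of OST-S.

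At stake is how a table reads that goes to the project officer in support of a funding supplement, with the trial's primary outcome measures as its content.

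**Working it through.** The plan gives no expected proportions for this analysis, so there is no figure of its own to reproduce. The check is on the rule itself.

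**Inputs from the documents (Protocol 6.2.2).** Cut-offs c = 0.20, 0.50 and 0.80. Denominator for the categories: SD of change in the student's own arm. Denominator for the group effect size: TAU-WL SD of change.

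**Assumed inputs (not in the documents).** Normally distributed gains, signed so that positive is the expected direction. TAU-WL: mean gain m0 = 0.2, SD s0 = 0.4 raw points. OST-S: mean gain m1 = 0.4, SD s1 = r × 0.4, with r from 0.8 to 1.5.

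**Step 1: raw cut-off.** Under the rule, the raw change needed in an arm is c × SD of that arm. For large change, TAU-WL needs 0.80 × 0.4 = 0.32 points. OST-S needs 0.256 at r = 0.8, 0.32 at r = 1.0, 0.40 at r = 1.25 and 0.48 at r = 1.5.

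**Step 2: proportion with large change.**

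- TAU-WL, either rule: 1 − Φ(0.8 − 0.2/0.4) = 1 − Φ(0.3) = 38.2%.
- OST-S, own-arm rule: 1 − Φ(0.8 − m1/s1).
- OST-S, common TAU-WL SD: 1 − Φ((0.32 − m1)/s1).

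| SD ratio r | OST-S, own-arm | OST-S, common | Difference, own-arm | Difference, common |
|---|---|---|---|---|
| 0.8 | 67.4% | 59.9% | 29 points | 22 points |
| 1.0 | 57.9% | 57.9% | 20 | 20 |
| 1.25 | 50.0% | 56.4% | 12 | 18 |
| 1.5 | 44.7% | 55.3% | 6 | 17 |

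Worked line for r = 1.25 (s1 = 0.5). Own-arm: 1 − Φ(0.8 − 0.8) = 50.0%, and 50.0 − 38.2 = 11.8. Common: 1 − Φ((0.32 − 0.4)/0.5) = 1 − Φ(−0.16) = 56.4%, and 56.4 − 38.2 = 18.2 (18.1 before rounding the proportions).

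**Step 3: when the sign reverses.** Under the own-arm rule, each arm's proportion depends only on its mean/SD. With positive gains in both arms, OST-S looks worse when m1/s1 < m0/s0, that is, when s1/s0 > m1/m0. Example with a true mean benefit: m1 = 0.25, m0 = 0.20, s1 = 0.6, s0 = 0.4, so that 1.5 > 1.25. Own-arm: 1 − Φ(0.8 − 0.25/0.6) = 35.1% vs 38.2%, with OST-S 3 points lower. Common: 1 − Φ((0.32 − 0.25)/0.6) = 45.4% vs 38.2%, with OST-S 7 points higher.

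**Step 4: SDs that differ by chance alone.** If the true SDs are equal and the 175 students split 87 to 88 (assumed; the Protocol does not give the split by arm), the square roots of the 2.5% and 97.5% F quantiles give a range for the sample SD ratio of about 0.81 to 1.24. If SDs were recomputed within Grade 5 (39 students, assumed 19 and 20), the range is about 0.62 to 1.60. These ranges ignore clustering by school.

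**The case against.** The strongest reply is that this is conditional. At a ratio of 1 the two rules agree exactly, and no change-score SDs are given. A ratio of 1.5 is at the high end. At 1.1, with the same assumed means, the differences are about 16 vs 19 points. With about 87 students per arm, the standard error of a difference in proportions near 35% is already about √(2 × 0.35 × 0.65/87) = 7 points before clustering. At moderate ratios the distortion is therefore within sampling noise. This stands as a limit on size. It does not make the rule sound, because the distortion comes on top of the noise and a common denominator removes it at no cost.

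Second, the same report shows raw means and SDs by arm and subgroup, so a careful reader could see unequal SDs and work back to the raw cut-offs. That is true, but the proportions would still be presented as a direct comparison.

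Third, a mean difference and an individual change may legitimately be scaled differently. That also stands: having two scales in one section is not itself the error. The error is a scale that differs between the arms being compared.

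A reader might go further and infer any of three things that the documents do not support:

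- **That the proportions are not comparable at all.** They are comparable as change relative to the spread of each student's own arm. That answers a different question from how many students improved by a given amount.
- **That the rule is biased against OST-S.** The direction depends on which SD is larger, and that is unknown.
- **That the rule decides whether the trial is extended or colours its conclusions.** Section 6.2.2 makes new power calculations depend on a signal of a main or interactive effect, bases them on a fixed effect size of 0.50, and does not name these proportions as the trigger.

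**Conclusion.** The point holds in conditional form. Whenever the arm SDs of change differ, the own-arm rule grades equal raw change unequally. It can shrink or inflate the difference between arms, or reverse it if the ratio of SDs exceeds the ratio of mean gains.

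Under the assumed values, the own-arm rule overstates the difference in large change by 7 points at a ratio of 0.8 (29 vs 22). It understates it by 6 points at 1.25 (12 vs 18) and by 11 at 1.5 (6 vs 17). These figures rest on normality and on means and SDs chosen for illustration; the true size and direction cannot be known from the documents.

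The consequence is limited to an exploratory, one-time descriptive table sent to the project officer in support of a supplement. The SAP's main results are unaffected. The change is worth making because the rule does not answer the question it is set and the correction is trivial; it is not a threat to the trial's inference.

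**What to change.** In the degree-of-change paragraph of Protocol section 6.2.2, replace the own-arm SD with a single denominator for all students: the TAU-WL SD of change scores, already used for the group effect size in the preceding paragraph. Use the same value for both arms in every tabulation, and state whether it is recomputed within subgroups.

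The combined baseline SD from the SAP's Cohen's d is not a drop-in substitute. It is also common to both arms, but a baseline SD and a change-score SD differ in size, so the 0.20, 0.50 and 0.80 cut-offs would then stand for different raw changes.

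The cost is one phrase and no new data. The categories will differ slightly from those now planned, and if the table has already been produced it may need to be rerun on the same data set. The statistician works with masked arm labels, so the control arm's SD has to be identified for this step, but the planned group effect size already requires that.

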Descriptive statistics will be computed separately in three samples. First, using an intent-to-treat approach all enrolled participants will be examined. Second, using a per protocol approach most of the participants involved in the study during the COVID-19 shutdown in the spring, 2020 will be excluded from the sample. The only participants affected by COVID-19 who will be included are those for whom the duration of time between the collection of the COSS-P and/or COSS-T was  $\geq$  8 weeks (56 days) and the collection of post-treatment data for the COSS-P and/or COSS-T data occurred within 3 weeks (21 days) of the first date of shutdown (March 16). Third, using a per protocol approach two groups of participants will be excluded: (a) those participants affected by COVID-19 described earlier in this paragraph, and (b) those participants in the OST-S arm for whom COSS-T data were collected after the fourth intervention session (note: study team persisted with efforts to collect data in order to minimize missing data), because the initial sessions are believed to be critical for intervention success. **In our original statistical analysis plan, we planned to conduct intent-to-treat analyses, but we did not include a plan to conduct per protocol analyses. We are requesting an amendment to conduct per protocol analyses, as indicated.**

These exploratory descriptive analyses will be conducted on one occasion and a report will be sent to the IES project officer. By conducting the analyses in this way, our team is adhering to the approved IRB protocol. We will not conduct any statistical analyses in addition to those outlined above. To minimize bias in conducting these descriptive analyses, the deidentified data set needed for these analyses will be exported from REDCap by a study coordinator and will only include information about study arm (which will be deidentified), grade-level subgroup, school subsidized lunch subgroup, child sex, COSS-P and COSS-T raw scores at baseline and post-treatment, and sample subgroup (intent-to-treat, per protocol excluding most participants affected by COVID-19, and per protocol excluding most participants affected by COVID-19 and those in the OST-S condition with delayed collection of COSS-T data). A study statistician will conduct the analyses using the data set with deidentified study arms, and he will report findings to the study coordinator who will indicate the identity of the study arms for interpretation of findings.

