Evaluation of Organizational Skills Training (OST)
Program for Upper Elementary Students

NCT03443323

June 5, 2022

Data Management and Analysis

Analyses followed the intention-to-treat (ITT, as randomized) principle to examine the effect of OST-T2 at post-treatment and follow-up. Time zero was established as the date of consent. All measures were scored according to published instructions, and mean item scores were used in analyses. If an item was missing, mean item scores for each scale were computed without the missing item. An examination of pre-specified baseline student-level covariates, indicated in Table 1, noted some imbalances between groups. For this reason, we rebalanced the data using inverse probability of treatment weights derived from a logistic regression with treatment assignment as the outcome and all covariates as predictors (Loux & Huang, 2023). Once weighted, the baseline covariates collectively produced no association with treatment assignment (Model $p = 0.99$). This balancing procedure was then used in all outcome models to adjust for student-level covariates.

The pattern of medication use to treat ADHD symptoms was similar across conditions. Caregiver-reported rates of student medication use at baseline were 18% for the OST-T2 condition and 23% for TAU/WL; rates were 14% for OST-T2 vs. 18% for TAU/WL at post-treatment, and 16% vs. 21% at 12-month follow-up. Overall, only 9% of students in each condition had a change in medication status at any point in the trial. As such, medication status was not controlled in the analyses.

Prior to analyzing outcome data, we found that actual administration dates of assessments (a) departed frequently from pre-specified times within each assessment period, (b) varied by the informant completing the assessments (caregivers, teachers), (c) varied between treatment arm, and (d) overlapped so that post-treatment data for some students were sometimes collected later than the 5-month follow-up data for others. Discrepancies in data collection from pre-specified times generally were due to variations among informants in response to data requests. For that reason, we preplanned to model time as a continuous variable and allow for non-linear effects of treatment assignment by means of restricted cubic splines with knots at pre-specified locations (Fitzmaurice et al., 2011).

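### The third preliminary-analysis sample excludes students with late teacher ratings from the OST-S arm only, so the arms are no longer comparable on that criterion

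*Protocol*

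**What the plan says.** Protocol section 6.2.2 computes the preliminary descriptive statistics in three samples.

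- The first is intention-to-treat: "First, using an intent-to-treat approach all enrolled participants will be examined".
- The second removes most students caught by the spring 2020 school shutdown, in either arm.
- The third makes two exclusions. Exclusion (a) is "those participants affected by COVID-19 described earlier in this paragraph", again in either arm. Exclusion (b) is "those participants in the OST-S arm for whom COSS-T data were collected after the fourth intervention session".

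The reason given for (b) is "because the initial sessions are believed to be critical for intervention success". A note explains why late forms exist at all: "study team persisted with efforts to collect data in order to minimize missing data". The description of the exported data set repeats the restriction to one arm: the third category of the sample flag leaves out "those in the OST-S condition with delayed collection of COSS-T data". No timing rule for TAU appears anywhere in the section.

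The same section forms a rough effect size in each sample: the between-arm difference in mean change divided by the TAU standard deviation of change. If the results suggest an effect, new power calculations follow, and the summary goes to the funder's project officer in support of a supplement. The text does not say which of the three samples decides whether an effect is suggested.

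**The concern.** A per-protocol exclusion tied to session number can remove students only from the arm that has sessions. TAU students whose teachers returned the form equally late stay in. The effect size in this sample therefore compares an OST-S group filtered on teacher response time with a TAU group that is not. If response time is related to how much a student's rating changes, the difference between arms contains a selection effect that randomisation does not balance.

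There are two side effects. Rule (b) removes the participant, so the parent-rated COSS-P is lost as well, although the trigger concerns only the teacher form. And section 6.2.2 gives the statistician coded arms to limit bias, whereas the sample flag can undo that coding.

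At stake is the reading of a preliminary report used to look for an effect and to seek funding, not the trial's final result.

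**Working it through.** **Inputs from the documents**

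- Rule (b) and its reason: Protocol 6.2.2.
- Session schedule: 16 sessions, typically two a week, over about 8 weeks (Protocol 3.1.3). The fourth session falls at 4 / 2 = week 2 of 16 / 2 = 8 weeks.
- TAU is assessed at the same four time points (Protocol 3.1.4), so a time-based cut-off can be applied there.
- Preliminary sample: 64 + 72 + 39 = 175 students (Protocol 6.2.1).
- Expected effect size: 0.50 (Protocol 6.2.2).

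The plan gives no number excluded and no power for the third sample, so there is no stated figure to reproduce.

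**Which assessment is meant.** Section 6.2.2 does not say. Every post-treatment form comes after the fourth session, so on that reading the rule would empty the OST-S arm. Baseline is the sensible reading.

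**What the rule does to the difference between arms.** Suppose a share f of students in each arm has a late baseline form. Let late students change s SD less than timely ones whatever their arm (selection; s may be negative). Let late OST-S students show a further c SD less change because their baseline already reflects some treatment (contamination). Let δ be the true difference among timely students. Then:

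| Sample | Expected OST-S minus TAU |
|---|---|
| All students | [δ − f(s + c)] − [−f·s] = δ − f·c |
| Late excluded in OST-S only | δ − [−f·s] = δ + f·s |
| Late excluded in both arms | δ − 0 = δ |

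The one-arm rule removes the contamination term and puts a selection term in its place. The two-arm rule removes both. Going from all students to the one-arm exclusion moves the estimate by f(s + c) = f × g, where g is the whole difference between late and timely OST-S students.

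**Illustrative size (f and g assumed)**

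- f = 10%, g = 0.2: 0.10 × 0.2 = 0.02 SD
- f = 20%, g = 0.5: 0.20 × 0.5 = 0.10 SD
- Widest range tried, f = 5–30% and g = 0.2–0.8: 0.05 × 0.2 = 0.01 SD to 0.30 × 0.8 = 0.24 SD

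**Simulation check.** 88 against 87 students, 4,000 runs, independent students without clustering, no treatment effect, and no contamination (c = 0, so g = s):

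| f | g | Excluded in OST-S only | Excluded in both arms |
|---|---|---|---|
| 10% | 0.3 | 0.028 | −0.002 |
| 20% | 0.5 | 0.098 | −0.002 |
| 30% | 0.5 | 0.154 | 0.003 |

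The one-arm column agrees with f × g (0.03, 0.10, 0.15).

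**The flag.** A student who is in the second sample but not the third can only have been removed by rule (b), and so must be in OST-S. One such student is enough to identify which coded arm is OST-S.

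**The case against.** The strongest defence is that the rule addresses a defect that only OST-S can have. TAU students receive no sessions in this period, so a late TAU baseline is not contaminated, while a late OST-S baseline would tend to understate change. This stands, and it is why the rule should be repaired rather than deleted. It does not justify the asymmetry: a time cut-off in both arms also drops the late OST-S baselines, without filtering one arm alone.

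Several stronger inferences are tempting, and the documents do not support them:

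- *That the rule favours OST-S.* Nothing links late forms to smaller change, and part of any rise in the OST-S mean would be the removal of contaminated baselines, which is wanted.
- *That slow response is a teacher trait equally common in both arms.* The SAP attributes departures from schedule generally to informants' response to data requests, but it also reports that timing differed between arms.
- *That the discarded COSS-P was on time.* Section 6.2.2 does not give its timing for these students.
- *That TAU is wholly unselected.* The COVID-19 exclusion applies to both arms.

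It is also fair to say that the stakes are limited. The analyses are labelled exploratory and run once, ITT is reported beside them, and the per-protocol samples are openly declared as an addition. Any new power calculation uses the fixed 0.50 and 15% attrition rather than this sample's estimate.

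**Conclusion.** The point holds as a minor one. In the third sample the arms are treated differently on a criterion unrelated to allocation, and removal of partly treated baselines cannot be told apart from selection on teacher response time. The shift is f × g, which is 0.02 to 0.10 SD under the assumed 10–20% and 0.2–0.5 SD. Against the expected 0.50 that is 0.02 / 0.50 = 4% to 0.10 / 0.50 = 20%. The ratio is rough, because section 6.1.4 states 0.5 in cross-sectional SDs whereas section 6.2.2 divides by the SD of change. Neither f nor g is documented, so actual size and direction are unknown.

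A reader might infer that the trial's efficacy conclusion is affected. It is not: the SAP's final analysis is ITT, has no per-protocol set, and models actual assessment times. The possible loss of usable COSS-P data and the weakness in masking follow from the wording alone and need no assumption about f × g.

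**What to change.** Amend exclusion (b) in section 6.2.2 as follows.

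1. State that it refers to the baseline COSS-T.
2. Define lateness by one elapsed-time cut-off for both arms, in days from consent (the SAP's time zero), set to the typical time of the fourth OST-S session. The documents do not give the gap between consent and the first session, so take the value from session records and fix it before change scores are examined. A paired school's session date is a poor substitute, because paired schools may not run concurrently and schools may drop out or be replaced.
3. Apply the exclusion to the COSS-T analysis only, and keep COSS-P on its own timing.
4. Report the number excluded in each arm.

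Once late students in both arms can carry the flag, it no longer marks OST-S by definition. If the one-arm rule is kept, label the sample as a non-randomised comparison and base no decision about an effect on it.

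The cost is amendment wording and some TAU ratings, probably few, though the documents give no count. A common cut-off will not match every group's fourth session, so a few contaminated OST-S baselines may remain. It also assumes that lateness relates to change similarly in both arms. The ITT sample and the SAP's final analysis do not change.

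### The preliminary analysis relies on coded arms, but an exported sample flag that excludes students from OST-S only can reveal which arm is which

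*Protocol*

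**What the plan says.** Protocol section 6.2.2 presents the coded-arm procedure as a protection: "To minimize bias in conducting these descriptive analyses, the deidentified data set needed for these analyses will be exported from REDCap by a study coordinator". The order of events is then set out. First, "A study statistician will conduct the analyses using the data set with deidentified study arms". The results go to the coordinator, and only at that stage does the coordinator say which code is which. So the arms are meant to stay unknown to the statistician until the findings have been handed over.

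The same section defines three samples:

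- The first is everyone enrolled.
- The second removes most students affected by the COVID-19 shutdown.
- The third makes the second sample's exclusions and also removes "those participants in the OST-S arm for whom COSS-T data were collected after the fourth intervention session".

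The list of exported variables includes both the coded arm and a sample-subgroup variable. The last level of that variable is defined by leaving out, in addition to most COVID-affected students, "those in the OST-S condition with delayed collection of COSS-T data".

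For the effect size, section 6.2.2 states that "the difference in mean change scores between study conditions will be divided by the standard deviation of the control group", meaning the TAU-WL standard deviation of change scores.

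**The concern.** Coding the arms only masks the analyst if nothing else in the file depends on the arm. Here one variable does. The late-COSS-T rule refers to intervention sessions, and TAU students have none during the study period, so it can remove students from one arm only.

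What is at stake is a safeguard that the plan states and may not deliver. Some judgement remains in this report. The change categories are anchored at values approximating .20, .50 and .80 without exact boundaries, no numerical definition of no change is given, and the signal that would prompt new power calculations is not defined. Those choices are better made by someone who does not know the arms.

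**Working it through.** The plan states no figure for this point, so there is nothing to reproduce. The check is set logic, followed by a short probability calculation.

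**Step 1: what the flag implies.** Write S2 for the second sample and S3 for the third.

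- S3 = S2 minus the late-COSS-T students.
- Late-COSS-T students are by definition in OST-S.
- So every student in S2 but not in S3 carries the OST-S code.

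Neutral names for the subgroup levels would not help, because the drop from S2 to S3 would still occur under one arm code only. No deliberate decoding is needed either. Section 6.2.2 asks for descriptive statistics by arm in each sample, so the planned tables would show the count falling in one coded arm and staying fixed in the other.

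**Step 2: whether another section prevents this.**

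- Nothing in section 6.2.2 withholds the flag or orders the three analyses.
- Section 3.2 refers to section 8.1.1 for blinding. The third paragraph there says only that schools will know their assignment when they are recruited again.
- The SAP does not mention masking.

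**Step 3: how likely at least one such student is.** Inputs:

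- Sample at the preliminary analysis: 64 + 72 + 39 = 175 (section 6.2.1).
- OST-S students: not given. I assume 88, about half of 175, from the 1:1 design.
- Late rate p among OST-S students: not given. I assume a range of 1% to 10%.
- Share removed for COVID: not given. I show 0% and an assumed 20%.

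With no COVID exclusion, the chance of at least one late student is 1 − (1 − p)^88. With 20% removed, independently of lateness, it is 1 − (1 − 0.8p)^88.

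| Late rate p | No COVID exclusion | 20% COVID exclusion |
|---|---|---|
| 1% | 1 − 0.99^88 = 58.7% | 1 − 0.992^88 = 50.7% |
| 3% | 1 − 0.97^88 = 93.1% | 1 − 0.976^88 = 88.2% |
| 5% | 1 − 0.95^88 = 98.9% | 1 − 0.96^88 = 97.2% |
| 10% | 1 − 0.90^88 = 99.99% | 1 − 0.92^88 = 99.9% |

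A simulation of 5,000 runs with 88 and 87 students and 20% COVID exclusion revealed the arm in 52%, 88%, 97% and 99.96% of runs at these four rates. It never pointed to the wrong arm.

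**Step 4: whether the effect-size divisor is a second leak.** Take an illustrative difference of 0.25 and change-score SDs of 0.5 and 0.6 in the two coded arms. The candidate effect sizes are 0.25/0.5 = 0.50 and 0.25/0.6 = 0.42. Both can be calculated without knowing the arms, and the right one chosen once the coordinator names TAU-WL. The change categories divide by the SD of the student's own arm, which also works with coded arms.

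**The case against.** The strongest reply is that little depends on this step. The report is produced once, is descriptive and exploratory, and its outputs are listed in advance with a commitment to run nothing else. The arms are in any case revealed for interpretation. No specific calculation has been shown to change if the analyst knows the arms. The final analysis in the SAP uses neither the third sample nor the TAU-WL change-score SD. It fits intention-to-treat mixed models and scales Cohen's d by the combined baseline SD. All of this stands, and it makes the point a minor one.

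It is also fair to say that the protocol never states that any late-COSS-T student exists, and that the first two samples could be analysed before the third is examined. The first part means the conclusion must be conditional. The second is true, but the plan does not require that order, and the single export hands over everything together.

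A reader might infer more than the documents support in four ways:

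- **That the TAU-WL divisor unmasks the analyst.** Needing a label to choose the final ratio does not disclose the label, as step 4 shows. The plan should simply say how the choice is made.
- **That an unmasked estimate would set the new sample size.** Section 6.2.2 lets a signal trigger power calculations but bases them on the original assumptions, including an effect size of .50 and 15% attrition.
- **That this is the only comparison of the arms on the primary outcome.** The SAP's final analysis compares COSS-P and COSS-T by arm as well.
- **That 175 of the planned 280 students (62.5%) measures the damage.** That is the share of planned enrolment covered by the report. It measures neither bias nor the chance of unmasking.

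**Conclusion.** The point holds in a limited form. If at least one OST-S student with late COSS-T data remains in the second sample, comparing the second and third samples by coded arm identifies OST-S with certainty. The masking that section 6.2.2 describes is therefore not assured.

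It would go too far to say that masking must fail, because the number of late students is not stated. At least one is likely: an exclusion was written for this group, and the accompanying note says that staff kept pursuing data to limit missingness. The probabilities above rest on an assumed arm split, late rate and COVID exclusion, and are only a guide.

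The effect is confined to the credibility of one exploratory descriptive report to the funder's project officer. No bias in any estimate has been demonstrated, and the final analysis is not affected.

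**What to change.** Stage the export in section 6.2.2:

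1. Give the statistician the coded arms with only the intent-to-treat and COVID-excluded flags. Lock those results, including the cut-offs for the change categories and the definition of no change.
2. Then release the third-sample flag, run that analysis, and describe it in the report as unmasked.
3. Keep the prespecified effect size. Compute it with each coded arm's SD of change and report the TAU-WL version once the coordinator has revealed the arms. No change of divisor is needed.

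The cost is one extra export and a two-step run in place of a single pass, with a few sentences added to section 6.2.2. The third sample stays unmasked whatever is done, since its definition depends on the arm.

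If the analysis has already been carried out, state in any report of it that masking of the statistician was not assured.
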